15.2 Demographic and Baseline Characteristics

The following demographic variables will be summarized: age, sex, race, height and weight, comorbidities, and home medications.

15.3 Analysis of Primary Endpoint

Primary analysis compares volume of blood products transfused in the first 24 hours of admission in patients without severe TBI (severe TBI is defined as GCS \leq 8 and evidence of brain injury on imaging) receiving whole blood versus component therapy during initial resuscitation.

For continuous variables including the primary endpoint, the statistical method will depend on the distribution of the data. If the data appears to follow a normal distribution, a t-test will be used, otherwise, a nonparametric Wilcoxon rank sum test will be used.

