1.2 Overview of Clinical Studies

The change in standard practice from whole blood transfusion, to fractionation and component transfusion, occurred after the 1970s because of concerns over resource utilization and safety. However, there was no evidence documenting equivalence between whole blood and components for trauma patients, and new data is now suggesting that whole blood may be superior for obtaining hemostasis and oxygen delivery for the acutely bleeding trauma patient.²²

The first evidence that whole blood may be superior to component therapy for trauma patients comes from military studies in Iraq and Afghanistan using fresh whole blood (FWB). FWB was initially used as a source of platelets, in addition to PRBCs and

plasma, when platelets were not available in far-forward military settings.²³ A retrospective analysis of prospectively collected data from all transfused patients at 6 forward surgical teams comparing standard component therapy to component therapy with whole blood substituted for platelets found that when adjusted for confounding variables, patients who received FWB had a significant survival advantage.²³ Of note, a subgroup analysis of patients who received “universal-donor” group O FWB (49%) versus type-specific product found there was no difference in mortality between these groups, and that there were no transfusion reactions.

Similarly, a retrospective analysis of 354 combat casualties transfused at least one unit of PRBCs compared standard component therapy with PRBCs, plasma, and warm FWB.²⁴ Patients who received whole blood had significantly lower transfusion volume requirements, and received significantly less preservative and anticoagulant additive volume, compared to patients receiving standard component therapy. 24 hour and 30 day survival was significantly higher in the whole blood group.

On the civilian side, a recent randomized controlled pilot trial compared whole blood leukoreduced with a non-platelet-sparing filter and stored for up to 5 days at 1-6°C, supplemented with warm stored platelets, to regular component therapy in severely injured patients predicted to require large volume transfusion.¹ There was a trend towards decreased plasma and platelet requirements in the whole blood group in the on-protocol analysis. In post hoc analysis use of whole blood was associated with a reduction in the amount of transfusion when traumatic brain injury was excluded.

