3 STUDY OBJECTIVES

3.1 Primary Objective

The primary objective is to assess the clinical efficacy of whole blood compared to component therapy for trauma patients requiring massive transfusion, as measured by volume of blood products transfused within the first 24 hours of admission.

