5 CRITERIA FOR EVALUATION

5.1 Primary Efficacy Endpoint

The primary objective is to assess the clinical efficacy of whole blood compared to component therapy for trauma patients requiring massive transfusion. Primary analysis will compare volume of blood transfusion within 24 hours of admission for patients without severe TBI (defined as GCS \leq 8 and imaging evidence of brain injury) for patients who received WB versus component therapy for initial resuscitation.

Secondary Efficacy Endpoints

The secondary objectives will evaluate the effect on survival; the development of multiple complications related to survival; and wastage data. The full list of secondary endpoints is as follows:

1. Volume of blood transfusion within 24 hours of admission for patients with severe TBI (GCS \leq 8 and imaging evidence of brain injury) and for entire cohort of patients.
2. Thromboelastography parameters including maximum amplitude, reaction time, alpha angle, fibrinolysis, and platelet function at 3 and 6 hours of resuscitation, after every 6 units of whole blood equivalent (WB or PRBCs) given, at the time of completion of resuscitation (time of last unit of blood product given), and on ICU days 1, 3 and 5.
3. 30-day mortality;

PI: [name]

4. Duration of need for renal replacement therapy, mechanical ventilation, ICU admission, and hospital stay;
5. Number of units of blood products transfused by component/product during first 24 hours of admission and total hospitalization;
6. Complications which include clinical coagulopathy, infection, venous thromboembolism, cerebrovascular accident, acute coronary syndrome, transfusion-related lung injury, transfusion-associated cardiac overload during total hospitalization;
7. Hemolysis as measured by haptoglobin, bilirubin, lactate dehydrogenase, and direct antiglobulin on ICU day 1;
8. Wastage of blood units

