- The incidence of adverse events will be evaluated including: death, clinical coagulopathy, hemolysis, infection, venous thromboembolism, cerebrovascular accident, acute coronary syndrome, transfusion-related lung injury, transfusion-associated cardiac overload.
- The occurrence of any whole blood transfusion given to patients other than adult male trauma patients will also be recorded
- In addition to ongoing monitoring and final analysis, an interim safety analysis when approximately 50% of patients have been enrolled will determine if there is a difference in adverse events as defined above between groups.
- The interim analysis will be performed by the independent medical monitor. The independent medical monitor, [name], is an emergency medicine physician with extensive experience in clinical investigation and has no relation to the study other than to monitor safety. The independent medical monitor has the authority to stop the study if safety concerns arise, including but not limited to evidence for the pre-specified stopping criteria (see Section 12.5, Stopping Criteria). [name] is also independent of the Blood and Blood Derivatives Committee.

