8 STUDY TREATMENTS

8.1 Method of Assigning Patients to Treatment Groups

Treatment groups are not assigned as this is an observational study. Treatment is determined by the eligibility of the patient (male or female) and the availability of whole blood when the patient presents. Adult male patients meeting eligibility who have

PI: [name]

received or will receive whole blood for traumatic resuscitation will be enrolled in the whole blood group. Enrollment of 49 patients receiving whole blood is planned. Adult male patients meeting eligibility criteria who present when whole blood is not available will receive component therapy and will be enrolled in the component therapy group. Enrollment of 49 control (component therapy group) patients is planned. Female patients meeting eligibility criteria will also be included in the component therapy group (see Section 6.1, Study Population, for rationale).

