9.1.7 Adverse Events

Information regarding occurrence of adverse events will be captured throughout the study. Duration (start and stop dates and times), severity/grade, outcome, treatment and relation to study drug will be recorded on the case report form (CRF).

Morbidity and mortality in this study population (patients requiring massive transfusion for trauma) is high.²⁹ Therefore we expect a relatively large number of adverse events, and resulting SAE reports, for reasons unrelated to the study.

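### Lower 24-hour blood volume is read as efficacy, although a patient who dies early usually enters the primary comparison as a low, favourable value

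*Protocol*

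**What the plan says.** Section 3.1 assesses clinical efficacy "as measured by volume of blood products transfused within the first 24 hours of admission". Section 5.1 repeats this as the primary endpoint: "Primary analysis will compare volume of blood transfusion within 24 hours of admission for patients without severe TBI". Section 15.3 fixes the comparison, "Primary analysis compares volume of blood products transfused in the first 24 hours of admission in patients without severe TBI", and the test: a t-test if the data look normal, otherwise a Wilcoxon rank sum test. Neither test is adjusted.

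Section 15.1 analyses every eligible enrolled patient who received at least one unit of blood and had TEG testing. Section 9.1.6 starts TEG sampling on admission. Survival to 24 hours is not a condition of entry.

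On the groups, section 8.1 says: "Treatment groups are not assigned as this is an observational study". Sex and whole blood stock decide the treatment. On mortality, section 9.1.7 says: "Morbidity and mortality in this study population (patients requiring massive transfusion for trauma) is high". Section 2.1 expects that whole blood may lower both transfusion needs and, in the end, mortality.

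Deaths are also followed outside the primary endpoint: 30-day mortality is a secondary endpoint (5.1), increased mortality at the interim is a reason to stop (12.5), and mortality is compared quarterly (15.4).

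**The concern.** Transfused volume stops accruing at death. A patient who bleeds to death in the second hour may have a smaller 24-hour total than a survivor with the same injury, and the primary test counts the smaller total as the better result. If early death rates differ between the groups, two errors are possible:

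- **Harm read as benefit.** More early deaths on whole blood can contribute to a significant reduction in volume.
- **Benefit masked.** If whole blood lowers both need and early death, the extra survivors keep accruing volume and can hide part of the reduction. The combat cohort in section 1.2 had lower volume together with better survival ("24 hour and 30 day survival was significantly higher in the whole blood group"), so masking is possible but not certain.

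Equal early death rates cannot be taken for granted in groups formed by sex and stock.

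**Working it through.** **The plan's own figure.** Enrolled 49 per group, less about 18 with severe TBI, leaves 49 − 18 = 31 per group (15.5, Sample Size). The synopsis claims 80% power at a type I error of 0.05. No difference or SD is printed, so the power cannot be reproduced. Assuming a two-sided test, it implies a standardised difference of (1.960 + 0.842) × √(2/31) = 0.71.

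**Inputs the documents do not give.** These are the early death rate by arm and the share of 24-hour need received before death. Both are assumed over ranges.

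**Model.** 31 per arm, 50,000 trials per scenario.
- Need = 10 × exp(0.8z), with z standard normal; multiplied by 0.55 on whole blood (WB) when a benefit is assumed. Without deaths this benefit gives 80.7% power, close to the planned 80%.
- logit P(death before 24 h) = a + 1.5 × 0.8z, with a solved to give each arm's death rate.
- Those who die receive a uniform fraction of need. All deaths stay in the analysis set.
- Wilcoxon test at two-sided 0.05, so 2.5% nominal in favour of WB.

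**No effect on need: percentage of trials significantly favouring WB**

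| Received by those who die | 15% v 15% | 20% v 15% | 25% v 15% | 35% v 15% |
|---|---|---|---|---|
| 10-50% of need | 2.4 | 4.9 | 8.7 | 23.0 |
| 30-90% | 2.4 | 3.3 | 4.5 | 8.3 |
| 60-100% | 2.4 | 2.7 | 3.2 | 4.2 |
| 100-200% | 2.5 | 2.0 | 1.7 | 1.1 |

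Death rates are WB v components. In numbers of deaths, 20% v 15% of 31 is 6.2 v 4.7, and 35% v 15% is 10.9 v 4.7. In the last row the sign reverses: results favouring components rise from 2.5% to 2.9%, 3.6% and 5.0%.

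**Benefit on need (×0.55), 10% deaths on WB v 20% on components**

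| Received by those who die | Plain Wilcoxon power | Deaths ranked worst |
|---|---|---|
| 10-50% | 63% | 73% |
| 30-90% | 77% | 73% |
| 60-100% | 80% | 73% |

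**How far a death-ranked analysis protects.** With no effect on need, this is the share of false WB-favouring results in which the death-ranked statistic does not favour WB:

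| Received by those who die | 20% v 15% | 25% v 15% | 35% v 15% |
|---|---|---|---|
| 10-50% | 17% | 36% | 69% |
| 30-90% | 3% | 9% | 42% |
| 60-100% | 0% | 3% | 20% |

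As a sole primary analysis it would be costly: at equal 20% mortality with 10-50% received, power falls from 82% to 48%.

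**Cross-check.** A second simulation used lognormal need with a coefficient of variation of 0.8, 5-50% received, deaths either independent of need or more likely at high need, and 8,000 trials per scenario. At equal death rates of 15% or 20%, two-sided Wilcoxon rejection was 4.5-5.0%. At 20% v 10% with no true effect, WB appeared to use 8-13% less blood, with 8-11% rejection, nearly all of it favouring WB.

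**The case against.** **The endpoint needs no extra rule.** A reader might infer that the endpoint is undefined for a patient who dies. It is not. Volume given within 24 hours exists for every such patient, and section 15.1 implies that the patient stays in if at least one unit was given and TEG was done. The TEG condition may remove some early deaths, but how many is not stated. The weakness is in how the value is read.

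**This is SAP detail.** Section 15 promises a SAP that may modify the analyses, and a table of 24-hour mortality is ordinary SAP content. That holds for the tables. It does not hold for the reading of lower volume as efficacy, which sections 3.1 and 5.1 already fix. The synopsis objective, which only compares volumes, is more neutral.

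**Excess deaths would be seen.** A reader might infer that harm could pass unnoticed. The documents do not support that. The interim mortality criterion, the quarterly comparisons and 30-day mortality all count early deaths, and the models in section 15.4 adjust for injury severity and shock. These safeguards make a silent misreading less likely. None of them changes the primary test or what its result is taken to mean.

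**The size is assumed and may be small.** This stands. The synopsis says initial resuscitation is generally over within hours, so a patient who dies later in the day may already have received most of the volume. The 10-50% case fits only very early deaths.

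**The death-ranked analysis is a weak guard.** This also stands, as the 3% and 9% figures show. It is useful only with 24-hour mortality beside it.

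**Conclusion.** The point holds conditionally. As the protocol is written, unequal early death can bias the primary volume comparison, usually in favour of the group with more early deaths. The direction reverses if those who die receive more than they would have needed as survivors. With equal early death rates there is no inflation, so a general claim that the test has an excess type I error is not supported.

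At a modest imbalance (20% v 15%), the false WB-favouring rate is about 2.0-4.9% against 2.5%. The 23% figure needs both a large imbalance (35% v 15%) and very early deaths. A reader might infer from it that the primary result is likely to be wrong. The documents give no early death rate or pre-death volume that would support this. All sizes rest on the assumed distribution of need, the death model and the fractions received. Severity is low to moderate; the direction of the mechanism is surer than its size.

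**What to change.** Keep the primary endpoint, test and sample size. In section 15.3:

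1. Report 24-hour mortality by arm beside the volume result.
2. Add one pre-specified supporting analysis of 24-hour volume with deaths before 24 hours ranked worst, reported whatever the primary result shows, and describe it as a partial safeguard.
3. State that lower volume is not interpreted as efficacy without reference to both.

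Time of death should come from the adverse event record. Section 9.1.7 says: "Duration (start and stop dates and times), severity/grade, outcome, treatment and relation to study drug will be recorded". Section 5.2 counts death among these events: "The incidence of adverse events will be evaluated including: death". The chart-review list in section 10.1 holds arrival date and time but only a date for death, so the event time must be completed for every death around the first day.

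The cost is a few lines of protocol text and one further analysis, with no new data item if event times are recorded as planned. The downside is a slightly more guarded efficacy claim. Worst rank is not proposed as the primary analysis because of the power loss shown above.

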STATISTICS Primary Analysis Plan	For continuous variables including the primary endpoint (volume of blood products transfused during the first 24 hours of admission), the statistical method will depend on the distribution of the data. If the data appears to follow a normal distribution, a t-test will be used, otherwise, a nonparametric Wilcoxon rank sum test will be used. To analyze coagulopathy over time a mixed effects linear regression model will be used. A mixed effects linear regression model will also be used to adjust for confounding variables such as sex, age, comorbidities, severity of injury, and physiologic parameters of shock including pH and temperature, and use of a rapid transfuser (which more effectively warms blood).
Rationale for Number of Patients	A sample size of 49 whole blood group (study drug) and 49 component therapy group (control) patients (98 patients total) is estimated. 18 of these per group are expected to have severe TBI and will be excluded from primary analysis, leaving 31 patients per group for the primary analysis. Using a Type I error rate of 0.05, and effect size based on reduction of PRBC and plasma transfusions described in the sensitivity analysis in a study by Cotton et al, 31 patients per group is expected to have 80% power to detect a significant difference in volume of transfusion in 24 hours. ¹

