6 PATIENT SELECTION

6.1 Study Population

All trauma patients who present with SBP<100 who require activation of the massive transfusion protocol and who do not have severe burns (>20% total body surface area) will be eligible for enrollment.

Enrollment of male and female patients:

PI: [name]

At UCLA and at least two other institutions²⁸ the standard of care for traumatic resuscitation for adult males is either:

- 1) Low anti-A anti-B titer (<1:100) group O+ whole blood
or, when whole blood is not available,
- 2) Component therapy, consisting of group O+ PRBCs, group AB or A plasma, and untyped platelets

The standard of care for adult females is component therapy, consisting of group O- PRBCs, group AB or A plasma, and untyped platelets. Group O- whole blood is not available at our institution at this time. During a critical traumatic resuscitation, it is often impossible to determine precise age and menopausal status before initiation of transfusion. In order to avoid any possibility of alloimmunization of reproductive-age females, the UCLA Blood and Blood Derivatives Committee has approved group O+ whole blood only for use in males.

The index and control groups in the study therefore consist of:

- 1) Index group: male trauma patients presenting with SBP<100 who require activation of the massive transfusion protocol and who do not have severe burns >20% TBSA who receive whole blood;
- 2) Prospective control group: Prospectively-identified cohort of patients who present during the study with SBP<100 who require activation of the massive transfusion protocol and who do not have severe burns >20% TBSA but who are either not eligible or not able to receive whole blood. This category consists of patients who are female (who are not eligible to receive whole blood) and male patients who present when whole blood is out of stock;
- 3) Historical control group: male trauma patients who presented with SBP<100 who required activation of the massive transfusion protocol and who did not have severe burns >20% TBSA who received component therapy for traumatic hemorrhage requiring massive transfusion protocol activation, during the 5 years prior to initiation of the study.

A mixed effects linear regression model will be used to adjust for confounding variables, including sex.

Enrollment of patients of unknown precise age:

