6.2 Inclusion Criteria

All trauma patients who present with SBP<100 who require activation of the massive transfusion protocol and who do not have severe burns (>20% total body surface area) will be eligible for enrollment. The study plans to include all such patients who present during the study period of approximately 2 years.

Within this group of patients, all adult male patients who received or will receive whole blood are eligible for inclusion in the whole blood group. All adult male patients who received or will receive component therapy initially are eligible for inclusion in the component therapy group. All adult female patients are eligible for inclusion in the component therapy group.

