9.1.4 Vital Signs

Body temperature, blood pressure, pulse and respirations will be recorded on admission and at least every 4 hours thereafter while the patient is in the ICU.

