Total fluids received in the first 24 hours

Data collected on initial 5 days of hospitalization:

Vital signs: systolic and diastolic blood pressure, heart rate, respiratory rate, oxygen saturation, temperature

Hemoglobin

Hematocrit

PI: [name]

White blood cell count
Platelet count
Sodium
Potassium
Chloride
Bicarbonate
Blood urea nitrogen
Creatinine
Glucose
Aspartate transaminase (AST)
Alanine transaminase (ALT)
Total bilirubin
Direct bilirubin
Alkaline phosphatase
pH
Lactate
PaCO₂ (arterial CO₂ partial pressure)
PaO₂ (arterial oxygen partial pressure)
Base excess
Prothrombin time (PT)
INR
Partial thromboplastin time (PTT)
Fibrinogen
Thrombin
Antithrombin Complex
Factor V
Factor VII
Factor VIII
Factor X
D-dimer
Lactate dehydrogenase (LDH)

PI: [name]

Haptoglobin

Data collected on entire hospitalization:

Procedures performed during hospitalization

Operations performed during hospitalization

Discharge date

Disposition

Discharge capacity

Date and cause of death if applicable

Comorbidities

Admission medications

Total hospital and intensive care unit length of stay

Number of days on ventilator

Number of days on dialysis

Number of days on vasopressor medications

Number and nature of operative procedures

Development of venous thromboembolism

Development of acute kidney injury

Development of acute respiratory distress syndrome

Development of liver failure

Suspected or confirmed transfusion reaction

Hemolytic transfusion reaction

Transfusion associated lung injury

Development of cardiac failure

Development of clinical coagulopathy

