15 STATISTICAL METHODS AND CONSIDERATIONS

Prior to the analysis of the final study data, a detailed Statistical Analysis Plan (SAP) will be written describing all analyses that will be performed. The SAP will contain any modifications to the analysis plan described in this protocol.

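### The primary analysis in 15.3 is an unadjusted t-test or Wilcoxon test, although every woman is a control and section 6.1 names sex as a confounder

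*Protocol*

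**What the plan says.** **Primary test.** Section 15.3 compares 24-hour volume between whole blood and component therapy in patients without severe TBI. The rule is "If the data appears to follow a normal distribution, a t-test will be used, otherwise, a nonparametric Wilcoxon rank sum test will be used". No covariate is mentioned.

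**How patients reach an arm.** Section 8.1: "Treatment is determined by the eligibility of the patient (male or female) and the availability of whole blood when the patient presents". Section 6.2: "All adult female patients are eligible for inclusion in the component therapy group". Section 6.1 describes the prospective controls as women plus men who arrive when whole blood is out of stock. Data set 1 in section 15.1, the primary one, is not restricted by sex.

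**Adjustment.** Section 6.1: "A mixed effects linear regression model will be used to adjust for confounding variables, including sex". A fuller statement, "A mixed effects linear regression model will also be used to adjust for confounding variables such as sex, age, comorbidities, severity of injury", continues with pH, temperature and rapid-transfuser use. It appears twice: in section 15.4, which covers secondary endpoints, and in the synopsis row headed Primary Analysis Plan.

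**Men only.** Data set 4 is the only male-only comparison. Its controls are historical, from the five years before the study.

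**Room for change.** Section 15: "The SAP will contain any modifications to the analysis plan described in this protocol".

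**The concern.** Sex is tied to treatment by design, not by chance: a woman cannot enter the whole-blood arm. A raw comparison of the arms therefore mixes the product effect with any difference between men and women in 24-hour volume. The protocol recognises this in section 6.1 but leaves the remedy out of the section that fixes the primary analysis.

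The bias could go either way. If women receive less volume than men, the control mean falls and a real saving with whole blood is partly hidden. If women receive more, a saving could appear where there is none. In an unblinded, non-randomised cohort the primary result should be the one that deals with the confounder the protocol itself names.

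**Working it through.** **1. The plan's own figures.** The sample-size text expects about 18 of 49 patients per group to have severe TBI, so 49 − 18 = 31 remain, as stated. The synopsis gives 80% power at a type I error of 0.05 with 31 per group. Neither an effect size nor an SD is printed, so the 80% cannot be checked directly. Working backwards for a t-test (two-sided 0.05 assumed, since sidedness is not stated; 60 df), 31 versus 31 at 80% power implies a standardised difference d = 0.723. This is an unadjusted two-group comparison.

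**2. Bias of the raw comparison.** Let f be the share of women among controls and g the female-minus-male difference in volume, in SD units. The whole-blood arm has no women, so with no product effect:

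expected whole-blood mean − expected control mean = −f × g.

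The protocol gives neither f nor g. The table assumes |g| = 0.3 or 0.5 SD, and 3, 6, 9 or 15 women among 31 controls. Rejection rates are from simulation under no product effect (normal data, 40,000 runs, nominal 5%).

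| Women / 31 | f | Bias at 0.5 SD | As share of d | t-test, 0.3 SD | t-test, 0.5 SD | Wilcoxon, 0.5 SD |
|---|---|---|---|---|---|---|
| 3 | 0.097 | 0.048 | 7% | 5.2% | 5.3% | 5.2% |
| 6 | 0.194 | 0.097 | 13% | 5.5% | 6.5% | 6.4% |
| 9 | 0.290 | 0.145 | 20% | 6.0% | 8.2% | 8.0% |
| 15 | 0.484 | 0.242 | 33% | 8.6% | 15.1% | 14.5% |

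A regression on arm and sex stays at 4.9 to 5.1% throughout. The loss in the other direction is also visible. At d = 0.723, if women receive 0.5 SD less, raw power falls from 80% to about 60% with 9 women and about 45% with 15.

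**3. What the sex-adjusted contrast is.** No woman receives whole blood, so women carry no information on the product effect within their sex. In a model with arm and sex only, the arm coefficient equals the difference in means between whole-blood men and control men. Women add residual degrees of freedom and, once other covariates enter, information on their slopes.

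**4. Power of that contrast.** With m control men, SE = √(1/31 + 1/m) in SD units, df = 62 − 3 = 59, noncentrality = 0.723 / SE.

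| Control men m | SE | Noncentrality | Power | d detectable at 80% |
|---|---|---|---|---|
| 28 | 0.261 | 2.77 | 77.9% | 0.743 |
| 25 | 0.269 | 2.69 | 75.4% | 0.766 |
| 22 | 0.279 | 2.59 | 72.3% | 0.794 |
| 16 | 0.308 | 2.35 | 63.7% | 0.877 |

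These figures take no credit for variance explained by other covariates, and no penalty for covariates that differ between the arms.

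**5. The form of the adjusted model.** The protocol calls it a mixed effects model. That suits coagulopathy measured repeatedly. The primary endpoint is one volume per patient at one site, and no random effect is evident for it.

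**The case against.** The strongest reply is that sex has not been overlooked. Adjustment is announced in 6.1, 15.4 and the synopsis, data set 4 compares men only, and section 15 lets the SAP modify the plan. Model form, transformation and the ranking of supportive analyses are commonly left to a SAP, which is not shown here. The figures also rest on an assumed share of women and an assumed sex difference; at 10 to 20% women the t-test's error rate is only about 5.2 to 6.5%.

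Much of this stands. The size is unknown and may be small, and details of the model can wait for the SAP. What it does not answer is that 15.3 already names the primary test, and that test ignores a confounder built into assignment. Data set 4 does not fill the gap: it exchanges the sex problem for a possible difference between calendar periods, and it is not primary.

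A reader might infer that the protocol leaves open which result decides. That goes too far. Section 15.3 is the section on the primary endpoint and names only the raw test, and the synopsis says the adjusted model will also be used. The natural reading is raw test primary, adjusted model supportive. The one textual tension is the synopsis heading against the placement in 15.4.

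A reader might also infer that the 80% power is wrong. The documents do not show that. It belongs to the unadjusted 31 versus 31 comparison and is simply not given for an adjusted one.

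**Conclusion.** The point holds as a should-fix. The primary analysis as written lets any sex difference in 24-hour volume into the estimated product effect, and the sex-adjusted model is classified differently in the synopsis and the main text. This follows from the text alone and does not depend on the simulations.

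The size cannot be fixed from the protocol, because neither the expected number of women among controls nor the sex difference in volume is stated. Under an assumed 0.5 SD difference, the harm is negligible with about 10% women and material with about 50%, where the 5% test rejects about 15% of the time under no effect. The documents do not support a claim that the trial's conclusion will be wrong, nor a claim about the direction of the bias. The power figures assume a two-sided 0.05 test and the d of 0.72 implied by the stated 31 per group.

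**What to change.** In 15.3 and the synopsis, make the primary analysis the prospective whole-blood versus component contrast in patients without severe TBI, fitted by ordinary linear regression. Adjust for sex and the baseline confounders that the protocol already names and collects: age, comorbidities, Injury Severity Score, and first admission temperature and pH. Then:

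- Decide how skewed volume will be handled before the data are seen, instead of choosing the method from how they look.
- Use only values known at admission in this model. Rapid-transfuser use is a feature of the transfusion being measured, so keep it for a supportive model.
- Keep the raw t-test or Wilcoxon test and data set 4 as supportive analyses, and make 15.4 and the synopsis agree.
- State that, because no woman receives whole blood, the sex-adjusted contrast is in effect a comparison among men. A separate prospective men-only analysis would add little.
- In the sample-size section, say that the 80% applies to the unadjusted 31 versus 31 comparison, give the expected number of male controls without severe TBI, and restate power for the adjusted contrast.

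The cost is wording in 15.3, 15.4, the synopsis and the sample-size section. Temperature is already taken at arrival ("Body temperature, blood pressure, pulse and respirations will be recorded on admission", section 9.1.4). pH is listed only under "Data collected on initial 5 days of hospitalization" in section 10.1, so the first admission value must be defined and flagged. The downside is that the stated power becomes less favourable. No added enrolment is required.
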